### **3.2 STUDY POPULATION**

The sample population is knee osteoarthritis patients assessed and found to be eligible to this study.

### **3.3 INCLUSION CRITERIA**

- Patients with osteoarthritis of the knee who are aged 35 to 75 years.
- Patients who had been diagnosed with primary knee osteoarthritis on the basis of medical evaluation (knee pain for most days of previous month and bony enlargement of the knee) and radiographic examination (Kellgren-Lawrence) of grade 2 or more.
- Patients who had an average pain intensity of 40 or more on a 100mm visual analogue scale in the 7 days before baseline assessment.
- Written informed consent obtained from patient

### **3.4 Exclusion Criteria**

- Patients with knee pain which caused by conditions other than knee osteoarthritis.
- Patients who had knee replacement surgery of the affected knee in the past year.
- Patients who had undergone psychological treatment or any other clinical study during the past 12 months.
- Patients who had been diagnosed with mental disorder, pregnancy or breastfeeding.

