### **2.5.3 TERTIARY PREVENTION**

Once a person has been diagnosed with OA, tertiary prevention strategies aim to reduce the complications of the disease, such as reducing pain and functional disability, and improving quality of life. Self- management program such as weight control, physical activity and education, cognitive behavioural therapy interventions, rehabilitation services, medical management, and surgical treatments are recommended according to the anatomical distribution, the phase and the progression rate of the disease. Hunter and Felson (2006) have recommended the hierarchy of OA treatment based on the severity of OA symptoms, (1) Non-pharmacological management including education, exercise, weight loss, appropriate footwear; (2) Non- pharmacological management including physiotherapy, braces, and begin pharmacological with simple analgesics such as paracetamol; (3) pharmacological management including NSAIDS, opioids, and aspirate are inject if effusion is present; and (4) Surgery including osteotomy, total joint replacement.

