## **CHAPTER 3 METHODOLOGY**

### **3.0 STUDY LOCATION**

This study will be conducted at Orthopaedic Clinic in government hospital, namely Hospital Putrajaya and Hospital Serdang.

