### **3.1 STUDY DESIGN**

This study is a 2 arm randomized clinical trial involving diagnosed knee osteoarthritis patients who are eligible to the study from February 2015 to July 2015 at Hospital Putrajaya and Hospital Serdang, Selangor, Malaysia, will be conducted. The sample population will be randomly divided into experimental and control groups by applying block randomization technique in a ratio 1:1. Random allocation will consider and eliminate the possible bias based on the socio- demographic characteristics of the patients. The experimental group will receive Cognitive Behavioral Treatment (CBT) provided with The Knee Book (Ministry of Health, 2013) added to standard routine care, whereas the control group will receive standard routine care only provided with The Knee Book and follow the same schedule of assessment as the experimental group. For standard routine care, patients need to attend their clinic and physiotherapy session as usual based on their fixed appointment date. A baseline measurement on patients' knee pain intensity, functional disability, psychological distress (depression, anxiety and stress), fear- avoidance beliefs, pain catastrophising and self- efficacy in pain management will be collected on respondents in both intervention and control group prior to the introduction of CBT. The efficacy endpoint will then be measured immediately, one month and six months after intervention. Figure 3.1 shows the schematic diagram of the study design.

[figure not shown]

Figure 3 Schematic diagram of the study design

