### 3.11 INTERVENTION PROTOCOL

Both the intervention and control group will receive standard routine care throughout the study. They have to attend clinic and physiotherapy session as usual on their fixed appointment date. However, the control group will be provided with The Knee Book (Ministry of Health, 2013) and not receive further intervention. Patients in the intervention group will be provided with The Knee Book (Ministry of Health, 2013) and to receive a three sessions of group Cognitive Behavioral Therapy (CBT) (each session will be last for two and a half hour) bi- weekly. The session will be held in a group of eight to ten patients and supervised by an experienced senior clinical psychologist ([name]) and a physiotherapist. The intervention will be delivered by physiotherapists and nurses who will receive at least one day of training specific to the trial from an experienced senior clinical psychologist with CBT experience. Each session will be audio- recorded with a written consent from the patients. Fidelity of the CBT session will be assessed for a random sample of recordings by the experienced psychologist with the Cognitive Therapy Rating Scale (Blackburn et al., 2000), which is a valid and reliable CBT rating scale. It has high internal reliability which is cronbach alpha 0.95 and good face validity. In addition, patients in the intervention group will assess the Client Satisfaction Questionnaire (CSQ-8) after the last session of group CBT received for measuring satisfaction with the therapy provided (Attkisson, 2012). It has high coefficient alpha (ranged from 0.83 to 0.93).

The outline of the Cognitive Behavioral Therapy module is prepared and modified based on Linton (2005). The CBT intervention will include an introduction, lecture (knowledge and insight), problem solving, skills training, homework assignments and a feedback of the session. An example of a knee OA patient will be applied throughout the intervention as a model for discussion and practice in problem solving, in order to enhance peer support and social bonding. Compliance with CBT is defined as attendance at the initial assessment and at least three subsequent sessions.

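### Section 3.4 excludes past-year knee replacement but not knee surgery already booked inside follow-up, so some six-month pain scores may reflect an operation and dilute the CBT comparison

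*Protocol*

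**What the plan says.** Section 3.4 lists four exclusions. One concerns surgery: "Patients who had knee replacement surgery of the affected knee in the past year". None concerns an operation that is planned or already dated.

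Other sections describe who can enter and what follows:

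- Setting (3.0): "This study will be conducted at Orthopaedic Clinic in government hospital, namely Hospital Putrajaya and Hospital Serdang".
- Severity (3.3): "radiographic examination (Kellgren-Lawrence) of grade 2 or more", and "Patients who had an average pain intensity of 40 or more on a 100mm visual analogue scale in the 7 days before baseline assessment". Neither criterion has an upper limit, so grade 4, labelled severe in section 2.1, is eligible.
- Treatment hierarchy (2.5.3): the fourth and last step is "Surgery including osteotomy, total joint replacement".
- Follow-up (3.1): "The efficacy endpoint will then be measured immediately, one month and six months after intervention".
- Concurrent care (3.11): "Both the intervention and control group will receive standard routine care throughout the study". Nothing restricts surgery.
- Withdrawal (3.8, Procedures): the stated grounds are psychiatric illness and pregnancy; surgery is not among them.
- Adverse events (3.8, Procedures): hospital admission counts as a serious adverse event.
- Analysis (3.13): intention-to-treat, with every randomised patient kept in the assigned arm.
- Primary outcome (3.9): knee pain intensity. Section 3.5 sizes the trial on its change within six months.

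**The concern.** The protocol already treats replacement of the study knee as relevant to eligibility when it lies in the past year. It does not ask the forward-looking question, although the patients come from orthopaedic clinics, where surgery is one of the treatments on offer. A patient with a fixed operation date inside follow-up can be randomised and, under intention-to-treat, stays in the primary comparison.

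Once such a patient is operated on, the knee pain score no longer says much about CBT. Two things follow on average: the mean difference between arms shrinks, and the scores within each arm spread more. Both lower power. If surgery also turned out more frequent or earlier in one arm, the six-month estimate would be biased. Without a dedicated record of knee surgery, the trial would struggle to show afterwards whether any of this had happened.

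**Working it through.** **Inputs from section 3.5:** means 20.68 and 16.54, SD 10.85, two-sided alpha 0.05 (1.96), 80% power (0.842), stated minimum 109 per group. The formula is for two groups, so I take 4.14 as the between-arm difference, as section 3.5 does.

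**Assumptions, not in the documents:** the share f of each arm operated on before the six-month visit, equal in both arms; no CBT effect in operated patients; and, in step 3 and the imbalance check only, a surgical gain g of 10 points.

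**Step 1. The protocol's own figure.**
Difference = 20.68 − 16.54 = 4.14.
n = 2 × 10.85² × (1.96 + 0.842)² / 4.14² = 107.9, so 108 per group against the stated 109.
With 109 per group, SE = 10.85 × √(2/109) = 1.470, and power = Φ(4.14/1.470 − 1.96) = Φ(0.857) = 80.4%. The stated figure reproduces to within one patient.

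**Step 2. Dilution alone.** The effective difference is 4.14 × (1 − f), with the SE unchanged.

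| f per arm | Difference | Power at 109 per arm | n per arm for 80% |
|---|---|---|---|
| 0 | 4.14 | 80.4% | 108 |
| 2% | 4.06 | 78.8% | 113 |
| 5% | 3.93 | 76.3% | 120 |
| 10% | 3.73 | 71.7% | 134 |

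**Step 3. Dilution plus added variance.** If surgery shifts the score by g, the variance becomes approximately 10.85² + f(1 − f)g². With g = 10:

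- f = 2%: SD 10.94, power 78.2%
- f = 5%: SD 11.07, power 74.7%
- f = 10%: SD 11.26, power 68.6%

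**Step 4. Dependence on the number analysed.** Section 3.8 speaks of allocating 300 names, which differs from the 262 in section 3.5. With 150 per arm and 20% lost, 150 × 0.8 = 120 remain. Then SE = 10.85 × √(2/120) = 1.401. Under dilution alone, power is 84.0% at f = 0, 82.5% at 2%, 80.2% at 5% and 75.8% at 10%. The larger number cushions the loss without removing it.

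**Step 5. Imbalance between arms.** Let f_C and f_T be the operated shares in the control and CBT arms. The observed difference is (1 − f_T) × 4.14 − (f_C − f_T) × g. With g = 10:

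- f_C = 15%, f_T = 5%: 0.95 × 4.14 − 0.10 × 10 = 2.93, below 4.14
- f_C = 5%, f_T = 15%: 0.85 × 4.14 + 0.10 × 10 = 4.52, above 4.14

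Bias can therefore run in either direction, and the documents give no basis for choosing one.

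**The case against.** The strongest case against is that this is a pragmatic comparison of CBT added to routine care. Routine care continues in both arms and may include surgery, and keeping such patients preserves generalisability. Randomisation balances booked patients on average. Entry starts at Kellgren-Lawrence grade 2, which section 2.1 labels minimal, and section 2.5 calls non-operative care first line for all knee osteoarthritis. Nothing shows that any eligible patient has an operation date. All of this stands. It makes the frequency unknown and the point minor, but it does not close the gap. Who may be randomised is fixed by the protocol's eligibility criteria and is not a matter left to an analysis plan.

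Four stronger readings are tempting, and the documents do not support them:

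- *A booked patient's outcome measures the operation and not CBT.* This can hold only for assessments after surgery. The immediate and one-month assessments may well come before it.
- *Surgery moves the pain score far more than CBT does.* It may, but no section gives a surgical effect.
- *The comparison is biased against CBT.* Participants know their arm, so CBT could influence who goes ahead with surgery. No section says that it does, or in which direction.
- *Surgery during follow-up is not captured at all.* Section 3.8 counts hospital admission as a serious adverse event, so an operation needing admission should surface there. What is missing is a dedicated item giving the date and side of knee surgery at each assessment.

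**Conclusion.** The point holds in limited form. Section 3.4 lets a patient with knee surgery already scheduled before the six-month assessment be randomised, and no other section prevents it. The expected consequence is dilution and extra variance, mainly at six months; bias is conditional on unequal surgery rates or timing.

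The size depends on a surgery rate that the documents do not give. On the protocol's own figures the loss of power from dilution is 1.6 percentage points at 2% operated (80.4 − 78.8), 4.1 at 5% (80.4 − 76.3) and 8.7 at 10% (80.4 − 71.7). This assumes 109 analysed per arm, equal shares in both arms and no CBT effect in operated patients. If few patients are booked, the effect is negligible. It is a useful refinement and not an error that undermines the design.

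**What to change.** Add an exclusion to section 3.4 for patients already scheduled at screening for surgery on the affected knee before the six-month assessment. Add one item to the follow-up questionnaire in section 3.12 for the date and side of any knee surgery since randomisation, so that surgery can be reported by arm. Intention-to-treat stays as in section 3.13: patients operated on after randomisation remain in their arm. Neither change directs any patient's treatment.

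The cost is one screening question and one follow-up item. The downside is slightly fewer eligible patients, and results that do not apply to patients already booked for surgery.

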### 3.5 SAMPLE SIZE ESTIMATION

The formula for calculating sample size in hypothesis testing by comparing means will be used (Lameshow et al., 1990):

$$n = \frac{2\bar{\delta}^2[Z_{1-\alpha/2} + Z_{1-\beta}]^2}{(\mu_1 - \mu_2)^2} \quad (\text{For continuous variable})$$

Where:

(a) Using an assumed expected outcome of **knee pain intensity decrease** within 6 months of therapy,

$\bar{\delta}$  = estimated standard deviation (assumed to be equal for each group) is 10.85 (Wideman et al., 2014)

$\mu_1$  = estimated mean knee pain score for at least 6 months is 16.54

$\mu_2$  = estimated mean baseline knee pain score is 20.68 (Wideman et al., 2014)

$Z_{1-\alpha/2}$  = standard error when  $\alpha = 0.05$  (95% Confidence Interval) = 1.96

$Z_{1-\beta}$  = standard error associated with power = 0.842 ( $\beta = 0.20$ )

Power ( $1-\beta$ ) = 80%

Effect size ( $ES\mu$ ) =  $\mu_1 - \mu_2 / \bar{\delta}$  where  $\bar{\delta}$  = pooled standard deviation =  $\sqrt{\delta_1 + \delta_2} / 2$

$ES\mu = 0.38$  which corresponds to  $n = 109$

Based on the above formula, the required minimum sample size for each group,  $n$  is **109**. To factor in 20% attrition, total required per group will be **131**; hence a total of **262** patients will be required for the sample in both groups.

(b) Using an assumed expected outcome of **functional disability decrease** within 6 months of therapy,

$\bar{\delta}$  = estimated standard deviation (assumed to be equal for each group) is 35.61 (Wideman et al., 2014)

$\mu_1$  = estimated mean functional disability score for at least 6 months is 59.50

$\mu_2$  = estimated mean baseline functional disability score is 74.38 (Wideman et al., 2014)

$Z_{1-\alpha/2}$  = standard error when  $\alpha = 0.05$  (95% Confidence Interval) = 1.96

$Z_{1-\beta}$  = standard error associated with power = 0.842 ( $\beta = 0.20$ )

Power ( $1-\beta$ ) = 80%

Effect size ( $ES\mu$ ) =  $\mu_1 - \mu_2 / \bar{\delta}$  where  $\bar{\delta}$  = pooled standard deviation =  $\sqrt{\delta_1 + \delta_2} / 2$

$ES\mu = 0.42$  which corresponds to  $n = 90$

Based on the above formula, the required minimum sample size for each group, n is **90**. To factor in 20% attrition, total required per group will be **108**; hence a total of **216** patients will be required for the sample in both groups.

(c) Using an assumed expected outcome of **depression level decrease** within 6 months of therapy,

$\bar{\sigma}$  = estimated standard deviation (assumed to be equal for each group) is 5.83 (Dear et al., 2013)

$\mu_1$  = estimated mean depression score for at least 6 months is 9.65

$\mu_2$  = estimated mean baseline depression score is 12.06 (Dear et al., 2013)

$Z_{1-\alpha/2}$  = standard error when  $\alpha = 0.05$  (95% Confidence Interval) = 1.96

$Z_{1-\beta}$  = standard error associated with power = 0.842 ( $\beta = 0.20$ )

Power ( $1-\beta$ ) = 80%

Effect size ( $ES\mu$ ) =  $\mu_1 - \mu_2 / \bar{\sigma}$  where  $\bar{\sigma}$  = pooled standard deviation =  $\sqrt{\bar{\sigma}_1 + \bar{\sigma}_2} / 2$

$ES\mu = 0.41$  which corresponds to  $n = 92$

Based on the above formula, the required minimum sample size for each group, n is **92**. To factor in 20% attrition, total required per group will be **111**; hence a total of **222** patients will be required for the sample in both groups.

(d) Using an assumed expected outcome of **anxiety level decrease** within 6 months of therapy,

$\bar{\sigma}$  = estimated standard deviation (assumed to be equal for each group) is 5.1 (Wiles et al., 2013)

$\mu_1$  = estimated mean anxiety score for at least 6 months is 9.44

$\mu_2$  = estimated mean baseline anxiety score is 11.80 (Wiles et al., 2013)

$Z_{1-\alpha/2}$  = standard error when  $\alpha = 0.05$  (95% Confidence Interval) = 1.96

$Z_{1-\beta}$  = standard error associated with power = 0.842 ( $\beta = 0.20$ )

Power ( $1-\beta$ ) = 80%

Effect size ( $ES\mu$ ) =  $\mu_1 - \mu_2 / \bar{\sigma}$  where  $\bar{\sigma}$  = pooled standard deviation =  $\sqrt{\bar{\sigma}_1 + \bar{\sigma}_2} / 2$

$ES\mu = 0.46$  which corresponds to  $n = 74$

Based on the above formula, the required minimum sample size for each group, n is **74**. To factor in 20% attrition, total required per group will be **89**; hence a total of **178** patients will be required for the sample in both groups.

(e) Using an assumed expected outcome of **fear- avoidance beliefs decrease** within 6 months of therapy,

$\bar{\delta}$  = estimated standard deviation (assumed to be equal for each group) is 6.2 (Lamb et al., 2010)

$\mu_1$  = estimated mean fear- avoidance beliefs score for at least 6 months is 11.20

$\mu_2$  = estimated mean baseline fear- avoidance beliefs score is 14 (Lamb et al., 2010)

$Z_{1-\alpha/2}$  = standard error when  $\alpha = 0.05$  (95% Confidence Interval) = 1.96

$Z_{1-\beta}$  = standard error associated with power = 0.842 ( $\beta = 0.20$ )

Power ( $1-\beta$ ) = 80%

Effect size ( $ES\mu$ ) =  $\mu_1 - \mu_2 / \bar{\delta}$  where  $\bar{\delta}$  = pooled standard deviation =  $\sqrt{\delta_1 + \delta_2} / 2$

$ES\mu = 0.45$  which corresponds to  $n = 77$

Based on the above formula, the required minimum sample size for each group,  $n$  is **77**. To factor in 20% attrition, total required per group will be **93**; hence a total of **186** patients will be required for the sample in both groups.

(f) Using an assumed expected outcome of **pain catastrophising decrease** within 6 months of therapy,

$\bar{\delta}$  = estimated standard deviation (assumed to be equal for each group) is 1.14 (Cardosa et al., 2012)

$\mu_1$  = estimated mean pain catastrophising score for at least 6 months is 2.20

$\mu_2$  = estimated mean baseline pain catastrophising score is 2.75 (Cardosa et al., 2012)

$Z_{1-\alpha/2}$  = standard error when  $\alpha = 0.05$  (95% Confidence Interval) = 1.96

$Z_{1-\beta}$  = standard error associated with power = 0.842 ( $\beta = 0.20$ )

Power ( $1-\beta$ ) = 80%

Effect size ( $ES\mu$ ) =  $\mu_1 - \mu_2 / \bar{\delta}$  where  $\bar{\delta}$  = pooled standard deviation =  $\sqrt{\delta_1 + \delta_2} / 2$

$ES\mu = 0.48$  which corresponds to  $n = 68$

Based on the above formula, the required minimum sample size for each group,  $n$  is **68**. To factor in 20% attrition, total required per group will be **82**; hence a total of **164** patients will be required for the sample in both groups.

(g) Using an assumed expected outcome of **self- efficacy in pain management increase** within 6 months of therapy,

$\bar{\delta}$  = estimated standard deviation (assumed to be equal for each group) is 11.59 (Dear et al., 2013)

$\mu_1$  = estimated mean self- efficacy in pain management score for at least 6 months is 32.28

$\mu_2$  = estimated mean baseline self- efficacy in pain management score is 26.90 (Dear et al., 2013)

$Z_{1-\alpha/2}$  = standard error when  $\alpha = 0.05$  (95% Confidence Interval) = 1.96

$Z_{1-\beta}$  = standard error associated with power = 0.842 ( $\beta = 0.20$ )

Power ( $1-\beta$ ) = 80%

Effect size ( $ES\mu$ ) =  $\mu_1 - \mu_2 / \bar{\delta}$  where  $\bar{\delta}$  = pooled standard deviation =  $\sqrt{\delta_1 + \delta_2} / 2$   
 $ES\mu = 0.46$  which corresponds to  $n = 73$

Based on the above formula, the required minimum sample size for each group,  $n$  is **73**. To factor in 20% attrition, total required per group will be **88**; hence a total of **176** patients will be required for the sample in both groups.

From the sample size estimation of the outcomes, the outcome measure of **knee pain intensity decrease** provides the **largest sample size (n = 131 per group)**, and this will be used as the sample size for this research study.

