3.	
Radiological clinical (combined) classification criteria
 
 
A. ACR clinical + radiological: list method: knee pain and OP and at least one of three: age >50 yr, stiffness<30 min, crepitus (for tree method see references)
 
B. JSN<math>\geq</math>1 with OP <math>\geq</math>1 in same compartment OR JSN <math>\geq</math>2 OR sum of OP score of both compartments <math>\geq</math>2 with symptomatic knee (subscale Knee Injury and Osteoarthritis Outcome Score, quality of life and two out of four additional subscale with cutoffs: QOL <math>\leq</math>87.5, pain <math>\leq</math>86.1, symptoms <math>\leq</math>85.7, activities of daily living <math>\leq</math>86.8, and sports and recreation <math>\leq</math>85.0)
 
C. Presence of radiological changes (K&L <math>\geq</math>2) in addition to symptoms or clinical signs (reported pain present longer than 1 month in the last 10 years)
 
D. K&L grade <math>\geq</math>2 for tibiofemoral compartment OR grade <math>\geq</math>2 OP or grade <math>\geq</math>2 JSN and grade <math>\geq</math>1 OP for patellofemoral compartment AND affirmative answer to the question: "On most days, do you have pain, aching, or stiffness in either of your knees?"
 

Abbreviations: JSN, joint space narrowing; OP, osteophyte (s); TFJ, tibiofemoral joint; PFJ, patellofemoral joint; ACR, American College of Rheumatology; OA, osteoarthritis; Clin. E, clinical classification criteria E; QOL, quality of life (knee-related).
	

arthropathies and stress fractures”. The imaging investigations are sometimes unnecessary due to these techniques do not define the clinical syndrome of OA. The United States Department of Health, Education and Welfare (1966) examined that there are 40% of OA patients do not show OA symptom but shown evidence with radiographic changes. Furthermore, patients with clearly diagnosed OA and without complicated chronic pain may do not need blood tests, due to its erythrocyte sedimentation rate (ESR) and c- reactive protein test (CRP) are within the acceptable range. However, other laboratory tests such as synovial fluid should be assessed to determine the “synovial fluid is sterile, without crystals and a white- cell count of less than 1, 500 cells per microliter” among OA patients (Bijlsma, Berenbaum & Lafeber, 2011).

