#### **2.5.3.1b PHYSICAL AND OCCUPATIONAL THERAPY/ AEROBIC AND MUSCLE-STRENGTHENING EXERCISES**

A randomized controlled trial on the effectiveness of manual physical therapy and exercise in patients with osteoarthritis of the knee showed significant improvement in reducing knee pain, stiffness, and physical disability function, and enhancing walking distance (Deyle, Henderson, Matekel, Ryder, Garber & Allison, 2000).

Perlman, Ali, Njike, Hom, Davidi, ... and Katz (2012) done a study on 125 patients with knee OA based on radiographic evidence of American College of Rheumatology criteria. The intervention group received an eight weeks of Swedish massage (30 or

60 minute weekly or biweekly). Results showed improvement knee pain and functionality in the 60- minute (once weekly) massage groups over six- months follow- up.

A Malaysian study on the effectiveness of passive joint mobilization has shown significant reduction in knee pain among 22 patients (mean age of 61.4 years) with sub- acute or chronic OA (based on clinically and radiographically evidence) (Azlin & Lyn, 2011).

Therapeutic exercise program can improve the functional ability and pain knee OA (Ytterberg, 1994) Although the exact exercise intensity best for OA patients still remained unclear, aerobic and muscle- strengthening exercises generally was consider the core aspect in management of OA patients (Roddy, 2005).

Transcutaneous electrical nerve stimulation (TENS) is the most commonly used form of electro analgesia in the treatment of early arthritis pain in the knee. Clinically TENS is applied at varying frequencies, intensities, and pulse durations of stimulation. When high-frequency TENS is applied at low intensity it is referred to as conventional TENS. The analgesic effect is immediate. Pain relief lasts while the stimulus is turned on, but it usually abates when the stimulation stops.

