### 3.12 DATA COLLECTION PLAN

A baseline measurement on patients' knee pain intensity, functional disability, psychological distress (depression, anxiety, and stress), fear- avoidance beliefs, pain catastrophising and self- efficacy in pain management will be collected on respondents in both intervention and control group prior to the introduction of CBT. The efficacy endpoint will then be measured immediately, one month and six months after intervention. A structured self- administered questionnaire which is validated and reliable would be used as the data collection tool.

The questionnaire would consist of eight sections, sections A to H (A: Patients' socio- demographic and clinical characteristics; B: knee pain intensity; C: functional disability; D: Psychological distress (depression, anxiety and stress); E: Fear-avoidance beliefs; F: Pain catastrophising; G: Self- efficacy in pain management). The measures will include:

*Knee injury and Osteoarthritis Outcome Score (KOOS)* (Roos & Lohmander, 2003) will be adapted for the measurement of knee pain intensity and functional disability. The KOOS was developed as an extension of the Western Ontario and McMaster Universities Osteoarthritis Index (WOMAC) with the purpose of evaluating short-term and long- term symptoms and function in subjects with knee injury and OA. It has 42 items in five separately scored subscales: pain, other symptoms, function in activities of daily living (ADL), function in sport and recreation and knee- related quality of life. However, only the pain, ADL and function in sport and recreation subscale will be adapted.

*Depression Anxiety and Stress Scale (DASS)* (Lovibond, 1995) will be adapted for the measurement of depression and anxiety outcomes. The DASS is a 21- item questionnaire which designed to measure symptoms of depression, anxiety and stress. Patients are required to rate the extent to which they have experienced in depression, anxiety and stress symptoms over the previous week.

*Fear- avoidance Beliefs Questionnaire (FABQ)* (Waddell, Newton, Henderson, Somerville, & Main, 1993). The FABQ is a 16- item questionnaire which had been modified to measure fear- avoidance beliefs among knee OA patients. It is designed to predict those patients that have high pain avoidance behaviour.

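### The section 3.5 sample size enters an assumed 20% baseline-to-6-month change as the between-arm difference, so its 80% power silently assumes no change in the control arm

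*Protocol*

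**What the plan says.** Section 3.5 announces its method thus: "The formula for calculating sample size in hypothesis testing by comparing means will be used". The formula printed is the one for two independent groups, and its result is called the minimum for each group. For knee pain, the outcome is framed as a decrease "within 6 months of therapy". The two means are:

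- mu1: "estimated mean knee pain score for at least 6 months is 16.54", with no source cited;
- mu2: "estimated mean baseline knee pain score is 20.68", attributed to a published knee osteoarthritis study.

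The SD is 10.85, two-sided alpha 0.05 and power 80%. This gives an effect size of 0.38, 109 per group, and 131 per group after an attrition allowance. The section ends by adopting the knee pain figure as the size of the trial, and section 3.9 makes knee pain intensity the primary outcome.

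The comparison itself is between arms. In section 3.1, "the control group will receive standard routine care only provided with The Knee Book", and routine care there includes the usual clinic and physiotherapy appointments. Section 3.3 requires average pain of 40 or more on a 100 mm scale before baseline. Section 3.12 says of the KOOS that it "will be adapted for the measurement of knee pain intensity and functional disability".

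**The concern.** A 6-month mean minus a baseline mean is a change over time within one group. The trial will compare two groups at the same time, so the quantity that governs its power is the CBT mean minus the control mean at 6 months. Section 3.5 never states a control mean or a control change. Putting the baseline value in that place assumes, without saying so, that controls do not change over 6 months.

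The plan gives reasons to doubt that. Controls keep receiving active care. Section 2.5.3.1b reports that a trial of "manual physical therapy and exercise in patients with osteoarthritis of the knee showed significant improvement in reducing knee pain". Patients selected for pain above a threshold also tend to score somewhat lower later, whatever they receive.

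This calculation alone fixes the size of the trial. A reader of 3.5 would believe that the between-arm comparison has 80% power, and could then read a null result as stronger evidence against CBT than it is.

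**Working it through.** **Inputs (section 3.5).** Baseline mean 20.68; 6-month mean 16.54; SD 10.85; z values 1.96 and 0.842.

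**1. Reproduce the stated figure.**
- Difference: 20.68 − 16.54 = 4.14. Effect size: 4.14 / 10.85 = 0.3816.
- n per group = 2 × SD² × (1.96 + 0.842)² / difference² = 2 × 10.85² × 2.802² / 4.14² = 107.9, so 108. With the effect size rounded to 0.38 it is 2 × 2.802² / 0.38² = 108.7, so 109 as printed.
- A two-sample t-test with 109 per group and a difference of 4.14 has 80% power.

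The arithmetic is sound. The question is what the difference stands for.

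**2. Where the 6-month means come from.** Ratio of 6-month to baseline mean in each calculation:

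| Outcome | Ratio |
|---|---|
| (a) knee pain | 16.54 / 20.68 = 0.80 |
| (b) functional disability | 59.50 / 74.38 = 0.80 |
| (c) depression | 9.65 / 12.06 = 0.80 |
| (d) anxiety | 9.44 / 11.80 = 0.80 |
| (e) fear-avoidance beliefs | 11.20 / 14 = 0.80 |
| (f) pain catastrophising | 2.20 / 2.75 = 0.80 |
| (g) self-efficacy | 32.28 / 26.90 = 1.20 |

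Every 6-month mean is the baseline moved by a flat 20%.

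**3. Power if controls also improve.** The protocol gives no control-arm change, so the following range is an assumption. Let controls improve by a fraction c of baseline while the CBT arm improves by 20% in total. The between-arm difference is then 20.68 × (0.20 − c). Power is for an unadjusted two-sample t-test with SD 10.85. The 150 per arm comes from the 300 names in section 3.8, with no loss.

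| c | Difference | SD units | Power, 109 per arm | Power, 150 per arm |
|---|---|---|---|---|
| 0% | 4.14 | 0.38 | 80% | 91% |
| 5% | 3.10 | 0.29 | 56% | 69% |
| 10% | 2.07 | 0.19 | 29% | 38% |
| 15% | 1.03 | 0.10 | 11% | 13% |

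**4. How much slack a larger analysed number gives.** The control improvement at which power is still 80% is 4.14 − 2.802 × 10.85 × √(2/n). That is about 0.4 points at 131 per arm and 0.6 points at 150 per arm.

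**5. What baseline adjustment could recover.** With an assumed baseline-to-6-month correlation r, the residual SD is 10.85 × √(1 − r²): 9.40 at r = 0.5 and 7.75 at r = 0.7. At 109 per arm, power is 68% (r = 0.5) or 84% (r = 0.7) with 5% control improvement, and 37% or 50% with 10%.

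**The case against.** Four counter-arguments deserve weight.

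*The 20% may be meant as the add-on effect of CBT.* The figure 16.54 has no citation; it is an assumed target, not an observed pre-post change. Both arms get routine care and the booklet and pass the same entry threshold, so gains common to both cancel in a randomised contrast. If 4.14 points is what CBT adds, power stays at 80%. This stands as a possible intention. However, 3.5 labels the two numbers as a baseline mean and a 6-month mean, which favours reading 20% as total change. The text should settle which is meant.

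*The control arm may be nearly stable.* Section 2.5.3.1a also cites a meta-analysis that found only a weak effect of education on pain, and the physiotherapy evidence concerns therapy given as a trial intervention, not continued appointments. This stands too: the documents do not refute a stable control arm. They leave the assumption unstated.

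*Saying that the power holds only if controls do not improve at all would be too absolute.* A reader might infer that, but more than 109 per arm may be analysed, and section 3.13 lists repeated measures ANOVA. At an assumed 120 per arm (150 less 20%) and a correlation of 0.7, a change-from-baseline comparison has 81% power with 5% control improvement. At a correlation of 0.5 it gains nothing over the unadjusted test (60%). Section 3.5 counts on none of this.

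*Scale and direction.* A reader might also infer that a fall from 20.68 to 16.54 is a worsening on KOOS, because a row of Table 1 in section 2.1 ("quality of life and two out of four additional subscale with cutoffs") treats low KOOS scores as symptomatic. The documents do not support that step. The row is a literature classification criterion, not the trial's scoring rule. Section 3.12 gives no scoring direction for the adapted instrument, and 3.5 does not name the scale behind its inputs.

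**Conclusion.** The point holds. Section 3.5 derives its 80% power from a change over time and applies it to a comparison between arms. The two coincide if the control arm is taken to stay at its baseline mean, or if 20% is the effect over and above control; the section states neither.

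If 20% is the CBT arm's total change, unadjusted power at 109 per arm falls from 80% to about 56%, 29% or 11% as controls improve by 5%, 10% or 15%. Those control figures are assumptions, as is the use of SD 10.85 throughout, and an analysis that uses baseline could soften the loss. The documents therefore do not show that the trial cannot detect a realistic difference. They show that the stated power rests on an undisclosed assumption to which it is very sensitive.

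On scale, the supportable statement is narrower than a wrong direction: the inputs carry no instrument name or direction, so they cannot be matched to the KOOS pain score in 3.12.

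**What to change.** In section 3.5:

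1. State the target as a between-arm difference in knee pain at 6 months: 4.14 points, 0.38 SD, for which 109 analysed per arm gives 80% power.
2. State the control-arm change assumed, and whether 20% is the CBT arm's total change or its effect over control.
3. Report power over a range of control-arm improvement, as in the table above. If the sponsor wants to count on a gain from baseline adjustment, give the correlation assumed.
4. Stop presenting the 20% within-arm change as what the trial is powered to detect. Apply the same wording to calculations (b) to (g).
5. Name the instrument, the scoring direction and the source of the SD for 20.68, 16.54 and 10.85, so that they can be matched to the KOOS pain score.

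The cost is a rewording of one section and a less favourable stated power. The restatement needs no extra patients.
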